11.4.4 Retention of Study Documents

According to ICH E6, Section 4.9, all CRFs, as well as supporting paper and electronic documentation and administrative records, must be retained for at least 2 years after the last approval of a marketing application and until there are no pending or contemplated marketing applications, or at least 2 years have elapsed since the formal discontinuation of clinical development of an individual product. Longer retention periods may apply. The IND Sponsor will notify investigators as to when documents no longer need to be retained. No study documents will be destroyed or moved to a new location without prior written

approval from the IND Sponsor. If the investigator relocates, retires or withdraws from the clinical study for any reason, all records required to be maintained for the study should be transferred to an agreed-upon designee, such as another investigator at the institution where the study was conducted.

Audit trails for electronic documents must be retained for a period at least as long as that required for the subject electronic records to which they pertain. The investigator must retain either the original or a certified copy of audit trails.

11.4.5 Data Confidentiality and Subject Anonymity

All information about the nature of the proposed investigation provided by the IND Sponsor or their representative to the investigator (with the exception of information required by law or regulations to be disclosed to the IRB, the subject or the appropriate regulatory authority) must be kept in confidence by the investigator.

The anonymity of participating subjects must be maintained. Subjects will be identified by their assigned subject number on CRFs and other documents retrieved from the site or sent to the IND Sponsor, study monitor, BMS, regulatory agencies, or central laboratories/reviewers. Documents that identify the subject (e.g., the signed ICF) must be maintained in strict confidence by the investigator, except to the extent necessary to allow auditing by the appropriate regulatory authority, the study monitor, IND Sponsor or their representative.

12. STATISTICAL CONSIDERATIONS

12.1. Study Design/Endpoints

Sample Size

This is an open-label, two stage, phase 2 study to evaluate the safety and clinical activity of nivolumab and relatlimab in patients with metastatic or locally advanced microsatellite stable (MSS) colorectal cancer that have a positive and negative composite PD-L1/Mucin (CPM). The primary endpoint is objective response rate (ORR) assessed using RECIST 1.1.

The trial will enroll two cohorts of MSS mCRC patients receiving 480mg nivolumab/160mg relatlimab: patients with MSS colorectal adenocarcinomas who have a positive CPM score (Cohort A); and patients with MSS colorectal adenocarcinomas who have a negative CPM score (Cohort B). The cut-off threshold $\geq 15\%$ of CPM will be used to determine CPM positivity. An additional cohort of MSS mCRC patients without biomarker selection will be enrolled to receive 480mg nivolumab/960mg relatlimab or 480mg nivolumab/480mg relatlimab (Cohort C).

Each cohort will enroll up to 32 evaluable patients. The primary endpoint is objective response rate (ORR) per RECIST 1.1, and the three cohorts will be analyzed separately for the primary analysis of rate of ORR. For each cohort, the treatment will be considered inactive and of no interest for further evaluation if the ORR is 5% or less and considered active if the ORR is 20% or

greater. This design allows for evaluating the efficacy of the treatment and CPM as a predictive marker simultaneously.

Simon two-stage minimax design is planned for each cohort. Initially, 18 patients per cohort will be treated in stage 1. Patients will be considered evaluable if they receive at least one dose of study treatment. If there is at least 1 response in that cohort then an additional 14 patients will be enrolled in stage 2 for a total of 32 patients in that cohort. If a total of 4 or more responses are observed in stage 1 and 2 combined, we conclude the regimen is promising and warrant further study. This design has 90% power to reject the null response rate of 5% in favor of 20% response rate, with one-sided type 1 error 0.1.

We expect that the prevalence of a positive CPM score is 10-15% among MSS CRC patients. Therefore, we will need to screen 220-320 MSS CRC patients in order to identify 32 marker positive MSS CRC patients. Assuming 95% of CRC patients are MSS, we will screen a total of 235-340 CRC patients.

Statistical Analyses

The primary endpoint is objective response rate, defined as complete response (CR) or partial response (PR) per RECIST 1.1. Objective response rate (ORR) will be estimated as the proportion of subjects whose best overall response is either a CR or PR with corresponding 95% CI. The primary population for the analysis is all subjects who receive at least one dose of study drug, and have at least one post-baseline tumor assessments or discontinue due to toxicity or clinical progression prior to post-baseline tumor assessments.

Exploratory endpoints include progression-free survival (PFS), overall survival (OS), and duration of response (DOR). PFS is defined as the time from the first day of study treatment to the date of the first documented tumor progression or death due to any cause, whichever occurs first. Subjects who did not progress or die will be censored on the date of their last tumor assessment. Kaplan-Meier curves will be used to summarize PFS. Overall survival (OS) is the time from the first day of study treatment to the date of death due to any cause. A subject who has not died will be censored at last known date alive. Kaplan-Meier curves will be used to summarize OS. Among patients with an objective response, DOR is defined as the time between the date of initial complete or partial response to the date of the first documented tumor progression or death due to any cause. Subjects who neither progress nor die will be censored on the date of their last tumor assessment. Summary statistics will be presented for DOR.

For biomarkers, potential relationships between biomarker data and efficacy or safety endpoints will be investigated aimed at identifying baseline biomarkers that may be used to prospectively identify subjects likely (or not likely) to respond to the treatment and to identify subjects who may be predisposed to having adverse reactions to treatment. These exploratory biomarker analyses will be completed with biomarkers measured in blood and in tumor samples.

The performance of the PD-L1/mucin composite score (CPM) in predicting treatment response will be further evaluated. ROC analysis based on logistic regression will be used to assess the

prediction accuracy, and the cutoff threshold for identifying patients who may benefit the therapy will be validated.

Genomic sequencing library construction, whole genome/exome sequencing, whole transcriptome sequencing, microbial sequencing, neoepitope prediction, mutation burden, and bioinformatic analysis will be performed either at an on-campus laboratory or at an off-campus sequencing service. All the samples will be de-identified before sending to any laboratory for sequencing. The FASTQ files, BAM files and VCF files will be generated and analyzed.

Genomic sequencing data will be stored and computations conducted using a JH IT managed subscription of Azure.

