Simon two-stage minimax design is planned for each cohort. Initially, 18 patients per cohort will be treated in Stage 1. Patients will be considered evaluable if they receive at least one dose of study drug. If there is at least 1 response in the initial 18 patients in a cohort, then an additional 14 patients will be enrolled in Stage 2 for a total of 32 (18 + 14 = 32) patients in that cohort. If a total of 4 or more responses are observed in Stages 1 and 2 combined, we conclude the regimen is promising and warrants further study. This design has 90% power to reject the null response rate of 5% in favor of 20% response rate, with one-sided type 1 error 0.1.

We expect that the prevalence of a positive CPM score is 10-15% among MSS CRC patients. Therefore, we will need to pre-screen 220-320 MSS CRC patients in order to identify 32 marker positive MSS CRC patients. Assuming 95% of CRC patients are MSS, we will pre-screen a total of 235-340 CRC patients.

The study will consist of a pre-screening period (for Cohorts A and B), a screening period (within 28 days of the first dose), a treatment period, and a follow-up period. Subjects will receive treatment on 28 day cycles, and will come to clinic for dosing and/or assessments on Day 1 of each cycle and additional days for safety and immune monitoring follow up as per the study schedule in **Section 9.** No dose escalations or reductions of nivolumab or relatlimab are allowed. Complete information on study drug administration, schedule, and dosing can be found in **Section 4.1.**

The study will include a safety run-in for the first six patients for Cohorts A and B only. If more than 1 of the first 6 patients experiences an unacceptable toxicity within the first cycle, then enrollment will be halted and the overall risk-benefit ratio of the study will be reconsidered. At any time thereafter, if more than 33% of patients are observed to experience unacceptable toxicity within the first cycle, enrollment will be halted and the safety of the combination will be reevaluated. Complete unacceptable toxicity criteria can be found in **Section 4.7**.

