3. PATIENT SELECTION

3.1. Eligibility Criteria

- 3.1.1. Age ≥ 18 years.
- 3.1.2. ECOG performance status of 0-1 (Appendix A).
- 3.1.3. Patients with histologically proven metastatic or locally advanced microsatellite stable (MSS) colorectal adenocarcinoma.
- 3.1.4. Cohort A: Primary lesion has a composite PD-L1/Mucin (CPM) score $\geq 15\%$.
- 3.1.5. Cohort B: Primary lesion has a composite PD-L1/Mucin (CPM) score < 15%.
- 3.1.6. Cohort C: Prior surgical resection of primary tumor. Prospective biomarker evaluation not required.
- 3.1.7. Patients who have received at least one prior cancer chemotherapy regimen in the locally advanced/metastatic setting. Adjuvant therapy can only be counted if recurrence occurred within 6 months of completing systemic chemotherapy.

- Radiosensitizing doses of chemotherapy are not considered systemic chemotherapy. Patients should be considered for standard therapies.
- 3.1.8. Presence of at least one lesion with measurable disease as defined by 10 mm in longest diameter for a soft tissue lesions or 15 mm in short axis for a lymph node by RECIST 1.1.
- 3.1.9. Patients must have available archival tissue from the surgical resection of their primary tumor for CPM score determination.
- 3.1.10. Patient's acceptance to have a tumor biopsy of an accessible lesion at baseline and on treatment if the lesion can be biopsied with acceptable clinical risk (as judged by the investigator).
- 3.1.11. Life expectancy of greater than 3 months.
- 3.1.12. Patients must have normal organ and marrow function as defined below:

 $\begin{array}{lll} \text{-} & \text{Leukocytes} & & \geq 2,000/\text{mm}^3 \\ \text{-} & \text{Absolute neutrophil count} & & \geq 1,500/\text{mm}^3 \\ \text{-} & \text{Platelets} & & \geq 100,000/\text{mm}^3 \\ \text{-} & \text{Hemoglobin} & & \geq 8.5 \text{ g/dL} \end{array}$

- Total bilirubin $\leq 1.5 \text{ x ULN}$ except subjects with Gilbert's

Syndrome, who must have normal direct

bilirubin

- AST(SGOT) and ALT(SGPT) $\leq 3.0 \text{ x ULN}$ - Albumin $\geq 2.8 \text{ g/dl}$

- Lipase and amylase < 1.5 x ULN Subjects with values > 1.5

ULN may enroll if there are neither clinical nor radiographic signs of a pancreatitis.

- Creatinine $\leq 1.5 \text{ x ULN or creatinine clearance (CrCl)}$

≥ 40 mL/min (if using the Cockroft-Gault

formula below):

Female CrC1 = (140 - age in years) x weight in kg x 0.8572 x serum creatinine in mg/dL

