8.1. Tumor Tissue Studies

Blocks or slides (twenty five unstained slides) will be collected from the surgical resection of each subject's primary tumor for CPM score determination as part of subject pre-screening (Cohort A and B only). CPM score determination for patients in Cohort C will be performed on archived samples at a later timepoint after enrollment. These slides will also be used for the evaluation of additional immune and tumor markers. Slides for CPM score determination will be stained with a hematoxylin and eosin (H&E) and PD-L1. See **Section 3.4** and the Laboratory Manual for additional details regarding tissue collection, processing, storage, and shipment.

Tumor biopsies will be collected (if the subject's tumor is thought reasonably safe and easy to biopsy) per **Section 9**. If a biopsy was done within 28 days before first dose, archived tissue from this biopsy may be used as a baseline sample. Fine needle aspiration samples do not contain sufficient tissue contextual information and will not be obtained. Additional biopsies may be obtained later in course of therapy.

To explore the association of the tumor microenvironment and clinical responses, archived tumor tissue and tumor tissue obtained at baseline and during treatment will be compared. PD-L1 expression may predict response to anti-PD-1 therapy[19]; however, PD-L1 is also upregulated in response to IFN-γ released by infiltrating T cells and could potentially be a predictor of response to any active immunotherapy. Pre- and post-treatment tumor biopsies will also be analyzed with immunohistochemistry and gene expression analysis for expression of T cell subset markers (CD3, CD4, CD8, FoxP3, Granzyme A/B, CD69), immune regulation (PD-L1, PD-L2, CTLA4, LAG-3, IDO1, TIM-3), and immune cell population markers (NK, DC, B cell, MDSC, M1/M2 macrophages).

To explore genetic determinants of response, whole-exome sequencing will be performed on DNA from tumors and matched normal tissue. We will characterize the tumor mutational landscape through exomic sequencing for mutation analysis and MANA prediction.

TCR sequencing will be undertaken to evaluate the T cell repertoire through next-generation sequencing in the tumor tissue for MANAFEST assay and to characterize peripheral immune responses to MANA. Gene expression profiling will also be employed to identify gene signatures within the tumor microenvironment (TME) associated with response and survival.

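### The CPM ROC analysis names no cohorts and does not allow for enrolment by CPM status, so specificity at the 15% cut-off could read about 0.40-0.68 against 0.87-0.92 in MSS CRC (exploratory, minor)

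*Combined protocol and SAP*

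**What the plan says.** Section 12.1 (Statistical Analyses) plans two things for CPM. "ROC analysis based on logistic regression will be used to assess the" accuracy with which CPM predicts response, and "the cutoff threshold for identifying patients who may benefit the therapy will be validated". No cohorts, analysis set, weights or dose term are attached to either. The efficacy population defined in that section belongs to the response-rate analysis. The statement that the three cohorts are analysed separately concerns the primary endpoint.

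Enrolment is by CPM status. Section 3.1.4 requires a score of at least 15% for Cohort A; Section 3.1.5 reads "Cohort B: Primary lesion has a composite PD-L1/Mucin (CPM) score < 15" per cent. Each cohort takes up to 32 evaluable patients under a two-stage rule: 18 first, then "If there is at least 1 response in that cohort then an additional 14 patients will be enrolled in stage 2".

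Cohort C is not selected on CPM. It is treated at relatlimab 480 or 960 mg, against 160 mg in A and B. It could enter the ROC, because "CPM score determination for patients in Cohort C will be performed on archived samples at a later timepoint after enrollment" (Section 8.1).

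On the target population, Section 1.4 states: "We expect that the prevalence of a positive CPM score is 10-15% among MSS CRC patients". Objective 1.3.3 concerns the CPM cut-off in patients with MSS CRC.

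**The concern.** A ROC curve plots sensitivity against one minus specificity, and judging a cut-off on it means reading those two quantities. Sensitivity is conditional on response and specificity on non-response. When patients are sampled on the marker, both depend on the ratio in which marker-positive and marker-negative patients were enrolled. That ratio is 1:1 in A+B if both fill, but between about 1:9 and 1:6 in MSS CRC at the protocol's prevalence.

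Read from an unweighted A+B curve, the 15% cut-off would appear to call nearly half of non-responders positive. In MSS CRC the share would be about 8-13%. Someone using the result to plan CPM selection in a later trial would be working from the enrolment ratio of this one.

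**Working it through.** **Inputs from the documents.** Up to 32 patients per cohort; stage 1 of 18, stopping at no responses; success at 4 or more of 32; response rates of 5% (inactive) and 20% (active); CPM-positive prevalence 10-15%.

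**Inputs assumed.** Response rate rp = 20% in CPM-positive patients and rn = 0-5% in CPM-negative patients. The documents give no rates by CPM status.

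**The plan's own figures first.** P(success) = sum over x = 1 to 18 of P(x responses in 18) × P(at least 4 − x in 14). At 20% this is 0.901 (stated 90%); at 5% it is 0.072, inside the stated 0.1. Screening: 32/0.15 = 213 and 32/0.10 = 320, against a stated 220-320. The design reproduces. The documents state no sensitivity, specificity or AUC.

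**Formulas**, with pos and neg the numbers above and below the cut-off:

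- specificity = neg(1 − rn) / [neg(1 − rn) + pos(1 − rp)]
- sensitivity = pos·rp / (pos·rp + neg·rn)

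**Specificity at 15%:**

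| ROC set, unweighted | rn = 5% | rn = 0% |
|---|---|---|
| A 32 + B 32 | 30.4/(30.4 + 25.6) = 0.543 | 32/(32 + 25.6) = 0.556 |
| A 32 + B 18 | 17.1/(17.1 + 25.6) = 0.400 | 18/(18 + 25.6) = 0.413 |
| A + B + C, 32 each, prevalence 15% and 10% in C | 0.656 and 0.672 | 0.668 and 0.683 |
| MSS CRC, prevalence 15% and 10% | 0.871 and 0.914 | 0.876 and 0.918 |

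The MSS CRC row at 10% and rn = 5% is 0.90 × 0.95 / (0.90 × 0.95 + 0.10 × 0.80) = 0.855/0.935 = 0.914. Leaving Cohort A out does not help: B+C gives 0.936-0.960, which is too high.

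**Sensitivity.** At rn = 5%, A+B gives 6.4/(6.4 + 1.6) = 0.80. MSS CRC gives 0.02/(0.02 + 0.045) = 0.31 at 10% and 0.03/(0.03 + 0.0425) = 0.41 at 15%. At rn = 2% the pair is 0.91 against 0.53-0.64; at rn = 0 there is no gap.

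**With the two-stage rule applied** (300,000 simulated trials of A+B, rates 20% and 5%, prevalence 12.5%), unweighted specificity averages 0.49 (5th-95th percentile 0.39-0.58). Weighting each stratum by target share over sample share (0.125/0.5 = 0.25 for A and 0.875/0.5 = 1.75 for B at 32+32) gives 0.893 (0.875-0.909). The true value is 0.893.

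**What weighting does for sensitivity.** Cohort B has no responder in stage 1 with probability 0.95^18 = 0.40 at rn = 5% and 0.98^18 = 0.70 at rn = 2%. Means when B has a responder:

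| rn | Unweighted | Weighted | True |
|---|---|---|---|
| 5% | 0.73 | 0.32 | 0.36 |
| 2% | 0.79 | 0.39 | 0.59 |
| 1% | 0.81 | 0.42 | 0.74 |

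Weighting helps at 5%, is no better in size of error at 2%, and is worse at 1%. About 7-8 responders are expected in A+B (7.67 at rn = 5%, 6.79 at rn = 2%).

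**Cohort C alone** has the MSS CRC mix, but 32 patients would include only 3.2-4.8 CPM-positive. The chance of no CPM-positive responder is (1 − 0.2 × prevalence)^32: 0.52 at 10% and 0.38 at 15%.

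**The case against.** The strongest objection is that the specificity gap mostly restates the enrolment ratio. When most patients do not respond, specificity is close to the CPM-negative share of the sample. A marker unrelated to response would score 0.50 in A+B and 0.85-0.90 in MSS CRC, not far from the figures for an informative marker. The weighted value therefore largely returns the prevalence put into it. This stands, and it is why a weighted specificity should never be shown without the non-predictive benchmark. It does not remove the concern, because the unweighted value is still wrong for the population named in objective 1.3.3.

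Second, the plan does not name sensitivity or specificity as outputs. Response rates within a CPM stratum, and fitted response probabilities at a given CPM, are not biased by the sampling; a threshold read from those would be safe. That is true, but the plan names a ROC analysis, and assessing a cut-off on a ROC curve uses the two affected quantities.

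Third, the per-cohort response rates with 95% CIs are already planned. This also stands, and the fix builds on it.

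A reader might infer more than the documents support:

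- That the AUC is biased, or the chosen cut-off displaced by a known amount. The documents give no CPM distribution, so neither can be shown.
- That the 15% value itself is unsound. The body of Section 3.4 is not visible in the public document, so its origin cannot be judged.
- That 0.54-0.56 is the specificity whenever Cohort A is included. It applies only to A+B with both cohorts full at 32.

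**Conclusion.** The concern holds in a limited form. Section 12.1 leaves the ROC set undefined and makes no allowance for enrolment by CPM status. A standard unweighted analysis that includes Cohort A would give specificity at 15% of about 0.40-0.68, depending on which cohorts enter and whether B stops at 18, against 0.87-0.92 in MSS CRC. Sensitivity would be overstated unless CPM-negative patients never respond. These figures rest on assumed response rates of 20% and 0-5% and on the protocol's 10-15% prevalence.

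Severity is minor. The analysis is exploratory and no decision rule depends on it. A reader might infer that the per-cohort go/no-go rules are compromised; they are not, since each cohort is tested on its own response rate.

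**What to change.** In Section 12.1:

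1. Name the cohorts in the ROC set: A+B (one regimen) as the main set, Cohort C shown separately.
2. Report specificity at 15% weighted to the CPM-positive share in MSS CRC. Show beside it the unweighted value and the value a non-predictive marker would give at that prevalence (one minus the prevalence). Use the pre-screen counts above and below 15% if usable; otherwise show results at both 10% and 15%.
3. Report weighted sensitivity as descriptive only, with its interval and the number of Cohort B responders. State that it is not estimable if there are none.
4. Base the statement on CPM as a marker on the per-cohort response rates and the A-minus-B difference with 95% CI. These do not depend on the sampling ratio.

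The cost is SAP wording and a little extra analysis; no procedure or sample size changes. Weighting assumes that enrolled patients resemble pre-screened patients within each CPM stratum. The calendar in Section 9.1 marks CPM at pre-screening and consent at screening, so use of the pre-screen counts must be confirmed; the 10%/15% fallback does not need them.

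The limits should be stated plainly. Weighting repairs specificity but not reliably sensitivity, and intervals will be wide. For example, 6/32 against 2/32 gives a difference of 12.5 points with a Newcombe 95% CI of about −5 to +30.

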1.3. Exploratory Objectives

- 1.3.1. To assess the overall survival (OS), progression free survival (PFS), time to-progression (TTP), disease control rate (DCR), best overall response (BOR), duration of response (DOR), duration of clinical benefit (DCB), and time to objective response (TTOR) of patients with metastatic or locally advanced microsatellite stable (MSS) colorectal cancer that have a positive and negative CPM score treated with nivolumab and relatlimab.
- 1.3.2. To assess immune objective response rate (iORR) by immune-related RECIST criteria (iRECIST).
- 1.3.3. To evaluate CPM score and determine the cut-off threshold as a predictive marker for I-O treatment in patients with MSS CRC.
- 1.3.4. To collect pre- and on-treatment biopsies to explore the association of features of the tumor microenvironment with response to therapy, including assessment of T cell subset markers (CD4, CD8, FoxP3, Granzyme A/B, CD69), immune regulation (PD-L1, PD-L2, CTLA4, LAG-3, IDO1, TIM-3), and immune cell population markers (NK, DC, B cell, MDSC).
- 1.3.5. To evaluate molecular determinants such as KRAS and BRAF status
- 1.3.6. To evaluate molecular determinants of response using next generation sequencing and other sequencing techniques.
 - Characterize the tumor mutational landscape through exomic sequencing for mutation analysis and MANA prediction.

- 1.3.7. To assess tumor burden dynamics using standard protein biomarkers when available as well as circulating biomarkers (i.e. ctDNA).
- 1.3.8. To collect peripheral blood lymphocytes to explore the association of lymphocyte activation markers with clinical response.
- 1.3.9. To evaluate clonal T cell populations in the tumor and in the periphery through T cell receptor sequencing, and to functionally assess mutation associated neoantigen-specific T cells.
- 1.3.10. To collect stool and oral wash (and/or buccal mucosal) samples at baseline and throughout treatment to explore the association of changes in the host microbiome and clinical outcome.
 - Microbial community analysis to correlate gut microbiome composition with response (OS, PFS and best overall response).
 - Whole metagenome functional profiling analysis via shotgun sequencing to correlate microbiome composition and microbial functions and pathways with response (OS, PFS and best overall response).

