Non-measurable disease: All other lesions (or sites of disease), including small lesions (longest diameter <10 mm or pathological lymph nodes with ≥10 to <15 mm short axis), are considered non-measurable disease. Bone lesions, leptomeningeal disease, ascites, pleural/pericardial effusions, lymphangitis cutis/pulmonitis, inflammatory breast disease, and abdominal masses (not followed by CT or MRI), are considered as non-measurable.

Note: Cystic lesions that meet the criteria for radiographically defined simple cysts should not be considered as malignant lesions (neither measurable nor non-measurable) since they are, by definition, simple cysts.

'Cystic lesions' thought to represent cystic metastases can be considered as measurable lesions, if they meet the definition of measurability described above. However, if non-cystic lesions are present in the same subject, these are preferred for selection as target lesions.

Target lesions: All measurable lesions up to a maximum of 2 lesions per organ and 5 lesions in total, representative of all involved organs, should be identified as **target lesions** and recorded and measured at baseline. Target lesions should be selected on the basis of their size (lesions with the longest diameter), be representative of all involved organs, but in addition should be those that lend themselves to reproducible repeated measurements. It may be the case that, on occasion, the largest lesion does not lend itself to reproducible measurement in which circumstance the next largest lesion which can be measured reproducibly should be selected. A sum of the diameters (longest for non-nodal lesions, short axis for nodal lesions) for all target lesions will be calculated and reported as the baseline sum diameters. If lymph nodes are to be included in the sum, then only the short axis is added into the sum. The baseline sum diameters will be used as reference to further characterize any objective tumor regression in the measurable dimension of the disease.

Non-target lesions: All other lesions (or sites of disease) including any measurable lesions over and above the 5 target lesions should be identified as **non-target lesions** and should also be recorded at baseline. Measurements of these lesions are not required, but the presence, absence, or in rare cases unequivocal progression of each should be noted throughout follow-up.

Evaluation of Target Lesions

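### The CPM ROC rests on a handful of responders, and an AUC taken from fitted logistic probabilities would be biased upward; compute it on the raw score in a fixed direction

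*Combined protocol and SAP*

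**What the plan says.** Section 12.1 (Statistical Analyses) says that the performance of CPM in predicting treatment response will be evaluated further: "ROC analysis based on logistic regression will be used to assess the" accuracy of prediction, and the cutoff for selecting patients will be validated. Response is CR or PR by RECIST 1.1. The exploratory objective in 1.3.3 is "To evaluate CPM score and determine the cut-off threshold as a predictive marker for I-O treatment in patients with MSS CRC". Sections 1.4 and 12.1 also present the design as evaluating treatment efficacy and CPM together.

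The plan does not say whether the ROC uses the raw score or the fitted probabilities. It gives no direction, interval, significance level or expected precision for this analysis.

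Three other statements bear on CPM without naming a model or comparison. Objective 1.3.1 lists OS, PFS, DCR and other outcomes in CPM-positive and CPM-negative patients. Section 12.1 plans to relate biomarkers to efficacy and safety endpoints in general. The cohort ORRs are estimated separately with confidence intervals. Section 8.1 adds that Cohort C will be scored for CPM later, on archived samples.

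Appendix C requires tumour size on a continuous scale: "A sum of the diameters (longest for non-nodal lesions, short axis for nodal lesions) for all target lesions will be calculated". Percent change in that sum is not an endpoint in Section 10 or 12 and is not linked to CPM.

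**The concern.** An AUC needs responders, and the plan's own rates promise few. The point estimate will be imprecise, and a cutoff that is both chosen and called validated on so few events could look far firmer than it is.

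The second problem is bias. With one predictor, the fitted logistic probability is a monotone function of CPM: rising if the estimated slope is positive, falling if it is negative. The AUC from fitted probabilities therefore equals the raw-score AUC in the first case and one minus it in the second. The data choose the direction that flatters the marker, and a useless score shows an average AUC clearly above 0.5. At stake is an over-optimistic report on a marker that takes 220-320 pre-screened MSS patients to study.

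**Working it through.** **1. The plan's own figure.** Section 12.1: "Initially, 18 patients per cohort will be treated in stage 1"; stage 2 adds 14, making 32; success means at least 4 responses overall. The trial stops at 0 of 18. P(reject) = sum over x ≥ 1 of Bin(x; 18, p) × P(Bin(14, p) ≥ 4 − x).
- p = 0.05: early stop 0.95^18 = 0.397; P(reject) = 0.072, within the stated limit of 0.1.
- p = 0.20: early stop 0.80^18 = 0.018; P(reject) = 0.901, matching "This design has 90% power to reject the null response rate of 5% in favor of 20% response rate".

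A search over designs returns this one as minimax. The primary design reproduces; it says nothing about the precision of the CPM analysis.

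**2. Expected responders for the ROC.** Expected number = n × ORR, 32 per cohort.
- Both 5%: 32 × 0.05 + 32 × 0.05 = 3.2 of 64 (2.6 of about 53 allowing for stage 1 stops).
- 20% and 5%: 6.4 + 1.6 = 8.0 of 64 (7.7 of about 58 with stops).
- Both 20%: 6.4 + 6.4 = 12.8 of 64.
- Adding Cohort C at the 20%/5% rates with 10-15% CPM-positive: its ORR is 0.10 × 0.20 + 0.90 × 0.05 = 0.065, up to 0.15 × 0.20 + 0.85 × 0.05 = 0.0725. That is 2.1-2.3 responders, so about 10 of 96, at different relatlimab doses.

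**3. Precision at AUC 0.70.** Hanley-McNeil: variance = [A(1−A) + (m−1)(Q1−A²) + (n−1)(Q2−A²)] / (mn), for m responders and n non-responders, with Q1 = A/(2−A) = 0.5385 and Q2 = 2A²/(1+A) = 0.5765. For m = 8, n = 56: (0.21 + 0.339 + 4.756)/448 = 0.0118, SE 0.109, 95% half-width 1.96 × 0.109 = 0.21.

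| Responders | 95% half-width |
|---|---|
| 3 of 64 | ±0.34 |
| 8 of 64 | ±0.21 |
| 13 of 64 | ±0.17 |
| 10 of 96 | ±0.19 |

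**4. Bias from fitted probabilities, no association.** The raw AUC has mean 0.5 and SD = √[(N+1)/(12mn)]. If the direction always favoured the marker, the mean would be 0.5 + SD × √(2/π). The logistic slope follows the difference in mean score rather than in ranks, so the simulated value is slightly lower.

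| Responders of 64 | SD | Upper approximation | Simulated, fitted | Raw score |
|---|---|---|---|---|
| 3 | 0.172 | 0.637 | 0.63 | 0.50 |
| 5 | 0.136 | 0.608 | 0.60 | 0.50 |
| 8 | 0.110 | 0.588 | 0.58 | 0.50 |

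With 3 responders, a useless marker reaches AUC 0.70 or more in about 26% of trials from fitted probabilities and 13% from the raw score. This step needs no model of tumour shrinkage.

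**5. Would tumour shrinkage do better?** Assumptions: 32 + 32 patients, ORR 20% vs 5%, two-sided 5%, a skewed CPM distribution. The documents give neither that distribution nor an SD for percent change.

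| How CPM acts | Rank test on response (ROC) | Spearman with percent change |
|---|---|---|
| Shifts shrinkage in all patients | 0.51 | 0.93 |
| Changes only who responds | 0.52 | 0.21 |

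A simpler comparison of A with B agrees in direction. Under a normal shift, d = 1.645 − 0.842 = 0.80 and power is 89% (t-test) against 28% (Fisher). If only the share of deep responders differs, it is 25% (t-test) or 17% (Wilcoxon) against 26% (Fisher).

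**The case against.** CPM evaluation is exploratory, and a ROC from logistic regression is a standard way to assess a classifier of response. The text does not say that the AUC comes from fitted probabilities. Even if it does, the sign of the coefficient and the separate ORRs of Cohorts A and B would show direction. All of that stands. It limits the bias point to a conditional one, and it rules out the inference that a wrongly directed CPM would go unseen; it does not remove the inflation of the AUC itself.

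A reader might also infer that CPM is judged by the ROC alone. It is not: other outcomes by CPM status are planned, though without a stated method.

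The most tempting stronger reading is that percent change in target lesions would answer the same question with far more power and should lead. The documents do not support this. The gain appears only if CPM shifts shrinkage across all patients, and step 5 shows a loss of more than half the power if it changes only who responds. Percent change also ignores new lesions and non-target progression, and it is missing for patients lost before the week 12 scan. Nor does it address the stated aims of predicting response and examining a cutoff.

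Finally, a power near one half for the ROC test is tied to two-sided 5%. At one-sided 0.10, the level used for the cohort tests, it is about 0.82. The plan sets no level for CPM.

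**Conclusion.** The concern holds in a limited form. The only CPM analysis with a named method will rest on about 3 to 8 responders of 64, about 13 if both cohorts are active, or about 10 of 96 with Cohort C. Those counts follow from the plan's own rates and, except where noted, full enrolment. The half-widths in step 3 are too wide to validate a cutoff.

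If the AUC is taken from in-sample fitted probabilities, it is inflated under no association by about 0.13, 0.10 and 0.08 at 3, 5 and 8 responders. That rests on the natural reading of Section 12.1, not on an explicit statement there.

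The shrinkage analysis is a sensible supplement whose value depends on an unknown mechanism; it should not replace the ROC. With no control arm, neither analysis can separate a predictive from a prognostic marker. The primary ORR tests are unaffected.

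**What to change.** In Section 12.1:
- Compute the ROC on the raw CPM score, with higher CPM pre-specified as predicting response, and not on fitted probabilities. Report the AUC with an exact or bootstrap 95% interval.
- State the expected number of responders and interval width, and describe the AUC and cutoff as descriptive instead of validated.
- As a supporting analysis only, add the Spearman correlation of CPM with best percent change from baseline in the target-lesion sum. Rank patients with no post-baseline scan because of toxicity or clinical progression as worst, in line with Section 10.1, which counts them as non-responders. Note that the measure ignores new lesions.

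The cost is a few sentences and one further analysis of measurements that Appendix C already requires. Sample size, patient procedures and the primary test do not change.
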